Research Protocol Summary

1. Protocol Title: Effects of rTMS on human brain activity measured with EEG and fMRI

Note: This protocol covers three studies (Aims 1-3) of a NIMH BRAIN R01 grant supporting this research currently under review.

2. Purpose of the Study:

Treating psychiatric and motor disorders without surgery or life-long pharmacology is a vexing but attainable goal. One avenue of progress has been the development of non-invasive brain stimulation methods such as repetitive transcranial magnetic stimulation (rTMS). This project investigates the effects of rTMS on neural circuits as a function of spatiotemporal parameters and brain state in order to better understand why the method works and how to improve its efficacy. Leveraging our expertise in application of TMS methodology during concurrent single neuron recording techniques in non-human primates and imaging and scalp potential techniques in humans (fMRI and EEG), we aim to resolve three interlocking problems in the design and application of rTMS: **stimulation frequency, spatial targeting, and interactions with brain state.**

Primary Objective: Investigate rTMS temporal parameters: impact of frequency (1Hz versus 5Hz versus 10Hz rTMS) and number of pulses.

Primary Endpoint: We make 2 general predictions. **(1)** 1Hz vs. 5/10Hz rTMS will have inhibitory vs. excitatory effects on behavior (reaction times—RTs) and motion-related (high vs low coherence) medial temporal (MT) activity (in both EEG, and fMRI). **(2)** Excitatory effects for 10Hz will increase with number of pulses.

Secondary Objective: Examine rTMS spatial targeting: recruitment of specific networks in either dorsal (rTMS-D) or ventral (rTMS-V) pathways.

Secondary Endpoint: We predict that compared to the control condition, rTMS-D will enhance motion task performance and motion-related (high vs. low coherence) activity in the dorsal pathway (e.g., FEF, IPS), whereas rTMS-V will enhance motion-related activity in ventral pathway, with little or no effect on motion task performance.

Tertiary Objective: Establish rTMS brain state-dependency: stimulation of active versus inactive regions.

Tertiary Endpoint: We predict that rTMS effects on MT activity will be potentiated during motion task blocks compared to both color task and rest blocks.

3. Background & Significance:

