Non-invasive methods for stimulating the human brain show great promise for safe, effective treatments of psychiatric and motor disorders, and are in widespread use for basic research on human behavior and cognition. One such method, transcranial magnetic stimulation (TMS), is the application of time-varying magnetic fields above the scalp that induce transient electrical fields in the brain. TMS clearly stimulates the brain and affects behavior, but we do not know why it works; its effects on neural activity within brain regions and networks are not understood at a biological level. This project seeks to determine the neural basis of effects caused by TMS as applied in sequences of pulses, known as repetitive TMS (rTMS), a technique approved by the FDA for the

treatment of depression, and currently used in multiple IRB approved protocols completed or in process at DUSOM (Pro00029516, Pro00040268, Pro00065334).

Furthermore, the therapeutic potential of rTMS has been limited by poor understanding of major factors determining its neural effects, including **stimulation frequency, spatial targeting, and brain state**. With respect to **frequency**, it is generally believed that low-frequency (~1Hz) rTMS produce inhibitory effects (Chen et al., 1997; Siebner et al., 1999; Muellbacher et al., 2000) and high-frequency rTMS ($\geq 2\text{Hz}$), excitatory effects (Fitzgerald et al., 2006; Leitao et al., 2013; Luber and Lisanby, 2014). However, there is evidence of low-frequency rTMS producing enhancements (Drager et al., 2004; Andoh et al., 2006; Andoh et al., 2008; Snyder, 2009; Caparelli et al., 2012) and high-frequency rTMS producing inhibition (Modugno et al., 2001; Lorenzano et al., 2002). Long rTMS trains are not optimal for interleaving rTMS with a behavioral task in order to modulate a specific neurocognitive process (Luber and Lisanby, 2014), and frequency effects for short rTMS trains (e.g., 3 seconds) could be quite different than for long rTMS trains. Also, it is unclear if the critical factor is the number of pulses or the duration of the pulse trains.

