2. *Motion period (3 s)*. The dots inside both circles start moving. All dots in the right circle move randomly in all directions (0% coherence—COH). Most dots in the left circle move randomly, but a percentage of dots move upward or downward together. The percentage of dots moving together is either high (18% coherence) or low (3% coherence) to make the task easy or hard (~90% or 60% correct, respectively, where chance=50%) as established in our pilot studies (Britten et al., 1992). Subjects indicate as quickly as possible whether the coherently moving dots in the left circle moved upwards or downwards through responses on two different buttons. Dot motion continues for 3 s regardless of response time. After the motion period, feedback for correct vs. incorrect responses is delivered: high- vs. low-pitch sounds (corresponding to high vs. low monetary payoffs at the end of the study).

3. *Inter-trial interval (ITI, mean: 4 s)*. Subjects maintain fixation on a central cross for a period varying between 2 and 7 sec (mean: 4 sec). This jittered ITI is critical for event-related fMRI analyses, but is also used to keep conditions identical.

Phosphene Threshold Determination: All rTMS procedures will occur in rooms 54210, 54211 and 54212 in the Department of Psychiatry and Behavioral Sciences, Duke Clinic South. Phosphene threshold is defined as the minimum magnetic flux needed to elicit phosphenes (the perception of moving lights in the absence of an actual visual stimulus) in 5 out of 10 trials. Like the motor threshold, phosphene threshold is a standard approach for determining the intensity of rTMS for each individual to reduce seizure risk. The phosphene threshold will be determined in a dark room using a blindfold to enhance the subject's ability to detect phosphenes. The presence of moving phosphenes will be identified by subject verbal response. The scalp region producing moving phosphenes will be identified and recorded on the BrainSight neuronavigation system. Phosphene and motion disruption threshold will be used to determine the exact location in V5 which is involved in motion perception; then intensity of stimulation over this specific area will be defined according to rMT. From this, we will confirm the target engagement.

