Study 1 investigates the effects of **frequency** and number of pulses, manipulated across blocks. Table 2 describes the 7 conditions used in this experiment. rTMS is applied to MT or the vertex at 7 doses consisting of up to 30 pulses at 1, 5, or 10Hz. In conditions 1–3, these frequencies are delivered for 3 seconds leading to 3, 15, and 30 pulses, respectively. In conditions 4 and 5, frequency remains at 10Hz, but durations are 1.5 and .3 seconds, respectively, to yield

Table 2. Conditions in Study 1

Cond	Sites	Hz	Sec.	Pulses
1	MT	1	3.0	3
2	MT	5	3.0	15
3	MT	10	3.0	30
4	MT	10	1.5	15
5	MT	10	0.3	3
6	Vtx	1	3.0	3
7	Vtx	10	3.0	30

numbers of pulses that match conditions 1 and 2. Thus, we manipulate frequency while keeping duration constant, and number of pulses while keeping frequency constant. In control vertex stimulation conditions 6 and 7, rTMS is delivered for 3 seconds at 1Hz or 10Hz, matching the pulses of conditions 1 and 3, respectively.

Each of the 7 conditions is assigned to two blocks of 20 trials each (40 trials/condition); each trial lasts 10 seconds, and we will administer 14 blocks (47 minutes, 280 trials total) in both the TMS-fMRI and TMS-EEG experiments. The TMS-fMRI and TMS-EEG will necessitate 60 minutes preparation to adjust the positioning for the TMS coil and—in the TMS—EEG experiment—apply the EEG cap, as well as 30 minutes for a brief rTMS side effect rating scale and visual analog mood ratings will be administered before and after each rTMS block. Thus, the entire session will last 3 hours for both the TMS-fMRI and TMS-EEG Session. As above, subjects' side effects will be monitored closely, and all side effect monitoring described above will be repeated. Furthermore, all intensities fall within the rTMS safety guidelines (Rossi et al., 2009b).

Study 2

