EEG analyses. Pre-processing of EEG includes bad channel replacement, temporal filtering, and ICA analyses to remove artifacts. EEG analyses use either repeated-measures ANOVAs or non-parametric methods (Maris and Oostenveld, 2007b, a) to infer amplitude and latency effects on relevant ERP components and/or sources, as described in each study. Coherence analyses are performed to estimate inter-channel connectivity, with planned analyses on cross-hemispheric and anterior-posterior associations. As done in our past studies, (Appelbaum et al., 2006; Appelbaum et al., 2008; Appelbaum et al., 2010; Ales et al., 2012; Appelbaum et al., 2012) depth-weighted minimum norm analyses will be performed using MRI-derived finite element head models calculated for each participant following alignment of electrode positions to the MRI head surface. Head models are based on compartmentalized tissue segmentations that defined contiguous regions for the scalp, outer skull, inner skull, and the cortex. Cortically constrained minimum norm source estimates are determined by a linear optimization of dipole magnitudes with the least total (root mean square) power while lead field normalization is used to compensate for the inherent bias toward superficial sources.

Specific Study Analytical Procedures

Study 1

TMS data: Mixed model ANOVAs with repeated-measures factors of Frequency (1Hz/5Hz/10Hz), and Number of Pulses (3/15/30 pulses), and rTMS (target, sham [vertex] stimulation) will be performed separately on the median RT and accuracy data. Power analysis shows that 30 subjects/group should be sufficient to see a medium sized effect at an alpha of 0.05. In our previous studies using a Working Memory task with active and sham rTMS over multiple sites, letter set sizes, and task phases, groups of 21 (Luber et al., 2007) 15 (Luber et al., 2008) and 26 (Luber et al., 2013) were sufficient to produce significant effects at the 0.05 level.

[figure not shown]
Study 2

DWI fiber tracking. Our DWI tractography methods have been reported (Davis et al., 2009). For a priori tracts connecting the MT cortex, we use TrackVis (trackvis.org) to identify MT and all connecting regions (FEF, IPS). (Kier et al., 2004b, a) FA values are extracted and analyzed using standard statistics.

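### Study 1's RT/accuracy factorial does not fit the seven conditions run, and its workable reductions test a different 10Hz-vs-1Hz comparison from the one the design describes

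*Combined protocol and SAP*

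**What the plan says.** The primary objective (section 2) is "Investigate rTMS temporal parameters: impact of frequency (1Hz versus 5Hz versus 10Hz rTMS) and number of pulses". The primary endpoint makes two predictions: "1Hz vs. 5/10Hz rTMS will have inhibitory vs. excitatory effects on behavior (reaction times—RTs", and "Excitatory effects for 10Hz will increase with number of pulses". Section 3 adds that "it is unclear if the critical factor is the number of pulses or the duration of the pulse trains".

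Section 4, Study 1, Table 2 lists seven conditions:

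| Condition | Pulses | Seconds | Hz | Site |
|---|---|---|---|---|
| 1 | 3 | 3.0 | 1 | MT |
| 2 | 15 | 3.0 | 5 | MT |
| 3 | 30 | 3.0 | 10 | MT |
| 4 | 15 | 1.5 | 10 | MT |
| 5 | 3 | 0.3 | 10 | MT |
| 6 | 3 | 3.0 | 1 | Vertex |
| 7 | 30 | 3.0 | 10 | Vertex |

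The same section summarises the design: "Thus, we manipulate frequency while keeping duration constant, and number of pulses while keeping frequency constant".

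Section 12, Study 1, gives the behavioural analysis: "Mixed model ANOVAs with repeated-measures factors of Frequency (1Hz/5Hz/10Hz), and Number of Pulses (3/15/30 pulses), and rTMS (target, sham [vertex] stimulation", run separately on median RT and accuracy. It names no contrast, no reduced model and no rule for empty cells. On size it says: "Power analysis shows that 30 subjects/group should be sufficient to see a medium sized effect at an alpha of 0.05".

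**The concern.** The analysis in section 12 reads as a 3 x 3 x 2 factorial, but the design in section 4 is an incomplete set of seven cells. The analyst will have to drop terms or cells, and section 12 does not say which. This is the only Study 1-specific analysis of RT and accuracy; MT activity falls under the shared fMRI and EEG analyses.

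The primary question is at stake. Pulses equal Hz times seconds, so one comparison of 10Hz with 1Hz holds duration fixed while pulses vary, and another holds pulses fixed while duration varies. If the choice is left open, a duration effect or a pulse effect can be reported as a frequency effect, depending on a decision that could be made after the data are seen.

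**Working it through.** **Stated sample size.** The figure of 30 per group comes without power, test, sidedness, effect-size metric or within-subject correlation, so it has no unique check. A paired contrast at d = 0.5, two-sided 0.05, has 75.4% power at n = 30 and needs 34 for 80%. A three-level repeated-measures ANOVA with f = 0.25 and an assumed correlation of 0.5 has 84.1% at n = 30 and needs 28. One common variant therefore agrees with the stated figure, and it is not called wrong here. The recruitment figure in section 6 reproduces: 38 / (1 - 0.20) = 47.5, rounded up to 48.

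**Cells.** The factors give 3 x 3 x 2 = 18 cells, of which 7 are run. Ignoring site, 5 of the 9 Frequency x Pulses cells are run.

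**Degrees of freedom.** The df of a term is the rank of the design matrix with the term minus the rank without it.

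| Model on the 7 cells | Columns | Rank |
|---|---|---|
| Frequency + Pulses + Site | 6 | 6 |
| + Frequency x Pulses | 10 | 6 |
| + Site x Frequency | 8 | 7 |
| + Site x Pulses | 8 | 7 |
| + both site interactions | 10 | 7 |
| Full factorial | 18 | 7 |

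Frequency x Pulses gains 6 - 6 = 0 df: the intercept and main effects (1 + 2 + 2 = 5) already use all five occupied Frequency x Pulses cells. Each site interaction gains 1 df, and both together also gain 1, so they are fully aliased. The three-way term gains 0.

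**What the 10Hz-vs-1Hz effect becomes** (numbers are condition means):
- MT-only additive model: 5 - 1.
- All conditions with one site interaction: 5 - 1.
- All conditions, additive: weights on conditions 1 to 7 are -0.75, 0, -0.25, 0, 1, -0.25, 0.25, that is (5 - 1) - 0.25[(3 - 7) - (1 - 6)].

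All three rest on the pulse-matched pair (3 pulses; 0.3 s against 3 s). The duration-matched version of prediction 1 is mean(2, 3) - 1.

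**How much the choice matters.** Assumptions: n = 38 completers (section 6), equal-variance errors, two-sided 0.05, effects at MT only, and dz = 0.5 for the full-range difference between two conditions. With contrast weights w and effect pattern s scaled 0 to 1, the noncentrality is

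λ = √n · dz · √2 · (w·s) / √(w·w), on 37 df.

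Patterns on conditions 1 to 5, with vertex at 0:
- log duration (0.3 to 3 s): 1, 1, 1, 0.699, 0
- log pulses (3 to 30): 0, 0.699, 1, 0.699, 0

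*Duration only:*
- 5 - 1: w·s = -1, w·w = 2, λ = -3.08, significant in 85%.
- Additive: w·s = -1, w·w = 1.75, λ = -3.30, 89%.
- mean(2, 3) - 1: w·s = 0, 5%.

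*Pulses only:*
- 5 - 1: w·s = 0, 5%.
- Additive: w·s = -0.25, λ = -0.82, 13%, with reversed sign.
- mean(2, 3) - 1: w·s = (0.699 + 1)/2 = 0.849, w·w = 1.5, λ = 3.02, 84%.

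Range over the assumed effect size (additive / 5 - 1 / mean(2, 3) - 1):

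| True effect | dz 0.3 | dz 0.5 | dz 0.8 |
|---|---|---|---|
| Duration only | 49 / 44 / 5% | 89 / 85 / 5% | 100 / 100 / 5% |
| Pulses only | 8 / 5 / 42% | 13 / 5 / 84% | 25 / 5 / 100% |

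**Whether the alternative can be estimated.** Conditions 1, 2, 3 (2 df), conditions 3, 4, 5 (2 df), and 1 vs 6 with 3 vs 7 (2 df) together have rank 6, which is all the between-condition df.

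**The case against.** Section 12 lists factors and writes out no interaction, and neither prediction needs Frequency x Pulses. Main effects can be fitted, both predictions can be estimated from the MT conditions, and sections 2 and 4 already state the comparisons of interest. On this view section 12 lacks only a cross-reference. All of these facts stand, so a reader should not infer that Study 1 cannot answer its primary questions. The objection does not remove the mismatch: the fitted main effect of Frequency is not the comparison that section 4 describes, and nothing in section 12 says which one governs.

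A reader might also infer that the plan shrinks an MT-only frequency effect to 75% of its size. That follows only from the all-condition additive model, which section 12 does not specify. With one site interaction, or with MT conditions alone, the estimate is exactly 5 - 1 and nothing is shrunk.

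Finally, the confounding is built into the design: pulses equal Hz times seconds, and section 3 admits the pulses/duration ambiguity. This stands too. New contrasts do not separate the three quantities. In the table above, the duration-matched contrast responds to a pure pulse effect in 84% of trials at dz = 0.5. The gain is that each contrast is chosen in advance and labelled with what varies.

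**Conclusion.** The point holds and should be corrected before analysis. The named factorial cannot be fitted on the seven conditions, and its workable reductions answer the pulse-matched question rather than the duration-matched one in section 4. The ranks and weights need no assumptions. The significance rates (85-89% against 5% for a pure duration effect; 5-13% against 84% for a pure pulse effect) rest on dz = 0.5, 38 completers, log-scaled effects and effects at MT only. They illustrate sensitivity and do not predict results.

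The documents do not support the stronger readings that no primary effect is estimable, that the sample size of 30 is wrong, or that a particular rule for attributing effects to frequency is required.

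**What to change.** Replace the factorial in section 12, Study 1, with a 7-level within-subject Condition factor, and pre-specify these contrasts for RT and accuracy:

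1. Condition 1 vs the mean of 2 and 3, labelled *duration fixed, pulses vary*.
2. Pulse trend at 10Hz over conditions 5, 4, 3, labelled *duration varies with pulses*.
3. Reported alongside: 5 vs 1 and 4 vs 2, labelled *pulses matched, duration differs*.
4. Vertex comparisons: 1 - 6, 3 - 7 and (3 - 7) - (1 - 6). An effect should not be called MT-specific on MT-only contrasts.

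State two limits: no single contrast isolates frequency from both pulses and duration, and conditions 2, 4 and 5 have no vertex control.

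The cost is SAP wording and narrower claims about frequency, with no new conditions, sessions or participants. If Holm is applied over contrasts 1 and 2, the first step is tested at 0.025. For a paired contrast at d = 0.5, power then falls from 0.85 to 0.77 at n = 38, or from 0.75 to 0.65 at n = 30. A formal rule for when a difference may be attributed to frequency is optional.

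### Low-cost improvement: analysing trial-level log reaction time, with coherence in the model, in place of one median per condition could add roughly 0 to 20 points of power at n=30

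*Combined protocol and SAP*

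**What the plan says.** The primary endpoint (section 2) predicts "inhibitory vs. excitatory effects on behavior (reaction times—RTs" for 1 Hz against 5/10 Hz, alongside effects on MT activity in EEG and fMRI. For Study 1, section 12 specifies "Mixed model ANOVAs with repeated-measures factors of Frequency (1Hz/5Hz/10Hz), and Number of Pulses (3/15/30 pulses" plus target versus vertex stimulation, and says these "will be performed separately on the median RT and accuracy data". The same outcome wording is used for Study 3. One median per participant and condition is the natural reading, although it is not spelled out.

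On the data behind each median, section 4 (Study 1) says "Each of the 7 conditions is assigned to two blocks of 20 trials each (40 trials/condition", run "in both the TMS-fMRI and TMS-EEG experiments". Whether the two sessions are pooled is not stated. In the shared motion task, "The percentage of dots moving together is either high (18% coherence) or low (3% coherence", with expected performance of "90% or 60% correct, respectively, where chance=50" percent. Coherence is not a factor in the Study 1 ANOVA, so as written each median mixes easy and hard trials. "Dot motion continues for 3 s regardless of response time", but no response deadline is given. The plan also gives no reason for the median, no transformation, no RT cut-off, no rule for missed responses, and no statement on whether error trials count.

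**The concern.** The prediction concerns a within-person shift in RT between stimulation conditions. With 40 trials per condition per session, trial-to-trial noise can be a sizeable part of the error in that contrast, and the summary statistic decides how much of the noise is averaged out. A median averages less efficiently than a mean on a scale where the data are roughly symmetric, and the log scale is the usual candidate for RT. The same participants and trials could therefore give a more precise test of the behavioral prediction. Mixing two difficulty levels in one median makes this worse, because the median then falls between two RT distributions.

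**Working it through.** **1. The plan's own sample-size figure.** Section 12 says 30 subjects per group suffice for a medium effect at alpha 0.05. It does not give the effect metric, test, sidedness or target power. Taking medium as a paired standardized difference d = 0.5 (mean difference divided by its SD), two-sided, the noncentral t gives 75.4% power at n=30, and 34 subjects are needed for 80%. Taking it as f = 0.25 in a three-level repeated-measures ANOVA with assumed correlation 0.5 gives 84.1% at n=30, with 28 needed for 80%. So 30 is consistent with one reasonable variant. Section 6 plans 38 completers: 48 × 0.8 = 38.4. At 38, the paired test has 85.1% power.

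**2. Trial-level information kept by the median.** For normal data the asymptotic efficiency of the median against the mean is 2/π = 0.64. Simulated ratios for 40 trials against mean log RT, with a proportional effect (shapes assumed):

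| RT shape | Information kept | Loss |
|---|---|---|
| Log-normal | 0.65–0.67 | about a third |
| Ex-Gaussian | 0.67–0.81 | 19–33% |
| Even mix of easy and hard trials, hard 1.4 or 1.8 times slower | 0.59, 0.41 | 41%, 59% |

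If only correct trials count and coherence is split evenly (assumed), about 20 × 0.9 + 20 × 0.6 = 30 trials remain per condition. The ratios barely change. Against the raw mean, the median loses little or nothing for ex-Gaussian RT: 0.86–0.93 for a proportional effect, 1.00–1.06 for a constant shift. The case is therefore for log RT, not for the plain mean.

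**3. From information to power.** The loss applies only to trial noise, not to person-to-person variation in the rTMS effect. Let w be the trial-noise share of the variance of the paired difference, for the measure on which d = 0.5 is set.

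- d = 0.5 set on log RT: d for the median = 0.5 / √[(1 − w) + w/0.64].
- d = 0.5 set on the median: d for log RT = 0.5 / √[(1 − w) + 0.64w].

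Example for the first case, w = 50%: 0.5 + 0.5/0.64 = 1.281, so d = 0.5/√1.281 = 0.442. Power is 64.8% against 75.4%.

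| Difference in power (points) | w=10% | 25% | 50% | 75% | 100% |
|---|---|---|---|---|---|
| n=30, d set on log RT | 2.3 | 5.6 | 10.6 | 15.1 | 19.1 |
| n=30, d set on median | 1.5 | 3.8 | 7.8 | 11.8 | 15.7 |
| n=38, d set on log RT | 2.0 | 4.9 | 9.6 | 14.0 | 18.1 |
| n=38, d set on median | 1.3 | 3.1 | 6.1 | 8.9 | 11.2 |

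**4. What w might be.** The documents do not say. Assume a within-person log-RT SD of 0.3. Trial noise in a difference of two 40-trial means is then 2 × 0.09/40 = 0.0045. With an effect SD between people of 0.04 log units (variance 0.0016), w = 0.0045/0.0061 = 74%. With 0.08 (variance 0.0064), w = 0.0045/0.0109 = 41%. Pooling to 80 trials halves the trial noise to 0.00225, and w falls to 58% and 26%.

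**5. Simulation checks (paired t, n=30).**

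- *No fast guesses, median tuned to d of about 0.5.* Log-normal or ex-Gaussian RT, hard trials 0, 25 or 50% slower, effect SD 0, 0.04 or 0.08, lapses 0 or 3%. The median had 71–79% power and mean log RT 76–95%. The gain was 4–21 points for effect SD 0 to 0.04 and 2–9 points for 0.08. Variants with a constant shift and a 3 s cap gave about 3–23 points at 40 trials and 0–23 at 80.
- *Trial share fixed, log-normal SD 0.4, 40 trials.* Median against mean log RT: 54% and 74% at about 100% trial noise, 66% and 76% at 50%, 77% and 75% at 25%. At the low share the gain is gone.
- *Fast guesses added (uniform 150–400 ms, median tuned to d = 0.5).* With 3% guesses and no cut-off, the median has 75–76% and mean log RT 69–75%. With 6% and no cut-off: 74–76% and 60–66%. With 6% and a 200 ms cut-off: 75–76% and 67–75%. With 6% and a 300 ms cut-off, mean log RT recovers to 75–87%.

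**The case against.** The strongest reply is that nothing here is an error. A repeated-measures ANOVA on medians is valid, and trial counts are equal across conditions by design. No bias or loss of type I error control is shown. That stands.

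A reader might infer that the study is underpowered because of the median. The documents do not support this. They do not say on which measure the medium effect was defined. If it was defined on median RT, the inefficiency is already inside the planned effect size, and what is at issue is a gain not taken.

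A reader might also infer that a third of the data is wasted outright. That holds only for trial noise, only for near-normal or log-normal RT, and only against log RT.

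It is tempting to add that robustness is not needed because RT cannot exceed 3 s. The protocol gives the duration of dot motion, not a response deadline. If there is a deadline, slow trials become omissions, and dropping them truncates log RT in the direction of the predicted slowing. Fast guesses are plausible too, with hard trials near 60% correct and instructions to respond quickly. As the simulations show, they can put the median ahead. This objection also stands, and it makes the remedy conditional on a cut-off and omission rule set beforehand.

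Two limits of scope remain. RT is one of several primary measures, and the paired contrast used here is simpler than the three-factor ANOVA in the plan.

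**Conclusion.** The median analysis is acceptable but probably not the best use of the trials collected. Relative to log RT it may lose up to about a third of trial-level information, with a larger loss if the two coherence levels are pooled in one median. The forgone gain is roughly 0 to 20 points of power at n=30. The top of that range needs trial noise to be nearly all of the error. The bottom applies when people vary widely in their response to rTMS, and pooling both sessions moves the gain toward it without necessarily removing it. Every power figure rests on assumed RT shapes, variances and guess rates, because the documents give none. The advantage depends on trimming: with frequent, untrimmed fast guesses the median can be the better choice. This is a recommended improvement, not a defect that threatens the trial's conclusions.

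**What to change.** In section 12, TMS data for Studies 1 and 3:

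- Make trial-level log RT the primary behavioral RT analysis, in a linear mixed model with a random participant intercept, random condition effects and coherence (high/low) as a factor. The random condition effects are essential: without them, trials are treated as independent evidence about the condition effect. If that model does not converge, use mean log RT per participant, condition and coherence level in the repeated-measures ANOVA, and state this fallback now.
- Fix the lower RT cut-off and the handling of no-response trials before the main data are analysed, using the planned pilot data and blind to stimulation condition. State whether error trials are included and whether the two sessions are pooled. Report omissions by condition.
- Keep median RT as a sensitivity analysis.
- In Study 3, apply this to the motion and color blocks only, with task difficulty as the high/low factor. Rest blocks involve fixation without a response and give no RT.

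The cost is SAP wording and slightly more analysis work, with no new data or participants. The downside to name in the plan is that log RT is more sensitive than the median to fast guesses and to truncated slow trials. The pre-set rules and the sensitivity analysis are there to guard against that. If the sponsor prefers the median, a stated reason and separate medians by coherence level would meet part of the point.
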